# 7.3. Medication Error and Special Situations Related to the Investigational Medicinal Products

Any administration of IMP that is not in accordance with the study protocol should be reported on the drug administration CRF, regardless of whether or not an adverse event occurred as a result.

The following are types of medication errors and special situations:

- 1. Medication error: Any unintentional error in the prescribing, dispensing, or administration of a medicinal product while in the control of the healthcare professional, patient, or consumer.
- 2. Overdose: Administration of a quantity of a medicinal product given per administration or cumulatively, which is above the maximum recommended dose according to the authorized product information. Clinical judgment should always be applied. Any dose of IMP (whether the test IMP, reference IMP, or placebo IMP), whether taken intentionally or unintentionally, in excess of that prescribed must be immediately reported to the sponsor. When the identification of the IMP is required, the investigator must follow the procedures for unblinding outlined in Section 5.9.2.
- 3. Misuse: Situations where the IMP is intentionally and inappropriately used not in accordance with the authorized product information.
- 4. Abuse: Persistent or sporadic, intentional excessive use of IMP, which is accompanied by harmful physical or psychological effects.
- 5. Off-label use: Situations where an IMP is intentionally used for a medical purpose not in accordance with the authorized product information.
- 6. Occupational exposure: Exposure to an IMP, as a result of one's professional or non-professional occupation.
- 7. Breastfeeding: Suspected adverse reactions that occur in infants following exposure to a medicinal product from breast milk.

## 7.4. Clinical Laboratory Tests

All clinical laboratory test results outside of the reference range will be judged by the investigator as belonging to one of the following categories:

- abnormal and not clinically significant
- abnormal and clinically significant

A laboratory test result that is judged by the investigator as clinically significant will be recorded both on the source documentation and the CRF as an adverse event and monitored as described in Section 7.1.2. An event may include a laboratory or diagnostic test abnormality (once confirmed by repeated testing) that may result in the withdrawal of the patient from the study, the temporary or permanent withdrawal of IMP or medical treatment, or further diagnostic work-up. (Note: Abnormal laboratory or diagnostic test results at the screening visit that preclude a patient from entering the study or receiving IMP are not considered adverse events.)

In addition, potentially clinically significant values may be predefined by the sponsor for selected laboratory test variables and, if so, will be documented in the statistical analysis plan or other relevant documents (eg, medical monitoring plan or laboratory analysis plan).

#### 7.4.1. Serum Chemistry, Hematology, and Urinalysis

Clinical laboratory tests (serum chemistry, hematology and coagulation, and urinalysis) will be performed at the time points detailed in Table 1. Clinical laboratory tests will be performed using the central laboratory. Specific laboratory tests to be performed are provided in Appendix K.

## 7.4.2. Other Clinical Laboratory Tests

#### 7.4.2.1. Human Chorionic Gonadotropin Tests

A serum  $\beta$ -HCG test will be performed for all WOCBP at screening (visit 1), and EOT or early termination (visit 8), and urine  $\beta$ -HCG tests will be performed for WOCBP at time points specified in Table 1. Any female patient who becomes pregnant during the study will be withdrawn. Procedures for reporting pregnancy are provided in Section 7.2.

#### **7.4.2.2.** Follicle-Stimulating Hormone Tests

Postmenopausal women will have a follicle-stimulating hormone (FSH) test at screening (visit 1).

#### 7.4.2.3. Saliva Collection

Saliva samples (~1 mL) will be collected using a standardized protocol available in the laboratory manual at time points described in Table 1. Care should be taken to freeze (at -70°C) the properly collected saliva samples as soon as possible (3-5 minutes) after collection from the patient. For additional details see Appendix N.

## 7.5. Physical Examinations

Physical examinations, including height (to be obtained at the screening visit only) and weight, will be performed at the time points detailed in Table 1. A full physical examination will include

the following: general appearance, head, eyes, ears, nose, throat, chest and lungs, heart, abdomen, musculoskeletal, skin, lymph nodes, and neurological systems. Any physical examination finding that is judged by the investigator as a potentially clinically significant change (worsening) compared with a baseline value will be considered an adverse event, recorded on the CRF, and monitored as described in Section 7.1.2.

## 7.6. Vital Signs

Vital signs (blood pressure [systolic/diastolic], body temperature, and pulse) will be measured before other assessments (eg, blood draws and administration of questionnaires) at the time points detailed in Table 1. All vital signs results outside of the reference ranges will be judged by the investigator as belonging to one of the following categories:

- abnormal and not clinically significant
- abnormal and clinically significant

Oxygen saturation and respiratory rate will be measured in cases of suspected anaphylaxis and severe hypersensitivity.

Before blood pressure and pulse are measured, the patient must rest in a supine or semi-erect/seated position for at least 5 minutes. The same position and arm should be used each time vital signs are measured for a given patient. For any abnormal vital sign value, the measurement should be repeated as soon as possible. Any vital sign value that is judged by the investigator as a clinically significant change (worsening) from a baseline value will be considered an adverse event, recorded both on the source documentation and the CRF, and monitored as described in Section 7.1.2.

# 7.7. Electrocardiography

A 12-lead ECG will be conducted prior to other assessments (eg, blood draws and administration of questionnaires) at the time points detailed in Table 1. The ECGs should be performed in triplicate with approximately 1 to 5 minutes between recordings after the patient has been supine for at least 5 minutes.

A qualified physician at a central diagnostic center will be responsible for interpreting all ECGs. ECGs, including those for unscheduled visits, should be performed and transmitted according to the central ECG reading instructions provided in the ECG user manual. ECG equipment will be provided to all investigational centers.

Although the ECG interpretation will be performed centrally, the clinical evaluation remains the responsibility of the investigator. The ECG will be evaluated by the investigator at the time of recording (signed and dated), and the printout should be kept in the source documentation file. All ECG results outside of the reference ranges will be judged by the investigator as belonging to one of the following categories:

- abnormal and not clinically significant
- abnormal and clinically significant

When potentially clinically significant findings are detected by the investigator, a cardiologist should be consulted for a definitive interpretation. Any abnormal findings assessed by the

investigator as a clinically significant change (worsening) compared with a baseline value will be considered an adverse event, recorded on the source documentation and in the CRF, and monitored as described in Section 7.1.2.

## 7.8. Immunogenicity

Blood samples (fremanezumab-treated patients only) for serum ADA assessment will be collected at the time points detailed in Table 1. Blood samples for ADA assessment will also be collected upon observation of any severe hypersensitivity reaction (eg, anaphylaxis). Bioanalytical personnel should be made aware of anaphylaxis occurrence as soon as possible in the event that an anti-fremanezumab immunoglobulin E assay is needed.

## 7.9. Assessment of Local Tolerability and Pain

Injection site assessments will be performed immediately (+10 minutes) and 1 hour (±15 minutes) after administration of each dose of the IMP (Table 1). The injection sites will be assessed for erythema, induration, and ecchymosis.

Severity will be graded according to the following criteria:

- Injection-site erythema, induration, and ecchymosis will be graded according to measurements: absent, 5 to ≤50 mm (mild), >50 to ≤100 mm (moderate), and >100 mm (severe). Induration must be assessed by careful superficial palpation, avoiding pressuring or squeezing the injection site.
- Spontaneous report of local pain after the injection will be measured as described in Table 4.

**Table 4:** Severity of Pain Scale for Injection Site Assessments

Symptom	Severity grade	Assessment
Pain	0	Absent
	1	Mild
	2	Moderate
	3	Severe

If a patient has severe injection site erythema, induration, ecchymosis, or pain at 1 hour after completion of IMP administration, the patient will be reassessed at 3 hours (±15 minutes) after completion of IMP administration and hourly (±15 minutes) thereafter, until the reaction is of moderate or less severity.

Appropriate treatment may be provided if necessary, in which case it must be recorded as concomitant medication.

Injection site reactions (injection site erythema, induration, ecchymosis, and pain) should be recorded as adverse events as described in Section 7.1.

## 7.10. Sport Concussion Assessment Tool 3rd Edition

The SCAT-3 is a standardized tool for the evaluation of injured athletes for concussion (McCrory et al 2009). It includes 8 metrics to measure concussion symptoms, including GCS, Maddocks Score, symptom evaluation, cognitive assessment, neck examination, balance examination, coordination examination, and Standardized Assessment of Concussion delayed recall. An adapted version of the SCAT-3 tool will be used.

Patients will complete the SCAT-3 questionnaire at the time points detailed in Table 1.

# 7.11. Two-Item Patient Health Questionnaire/Nine-Item Patient Health Questionnaire

The Patient Health Questionnaire is a 9-item questionnaire with each item corresponding to 1 criterion of the Diagnostic and Statistical Manual for Mental Disorders 4th edition diagnostic criteria for major depressive disorder. Each of the items is scored on a scale of 0 ("not at all") to 3 ("nearly every day") based on the frequency of symptoms (Spitzer et al 1999). The PHQ-2 was developed from the PHQ-9 to rapidly screen for depression. The PHQ-2 and the PHQ-9 are validated measures for detecting and monitoring depression, anxiety, and somatization (Kroenke et al 2010).

Patients will complete the PHQ-2 at the screening visit (visit 1) and the end of treatment or early termination visit (visit 8). If the PHQ-2 is positive (ie, a score of  $\geq$ 3), patients will complete the PHQ-9.

# 7.12. Assessment of Suicidality

The study population being administered fremanezumab should be monitored appropriately and observed closely for suicidal ideation and behavior or any other unusual changes in behavior. Consideration should be given to discontinuing fremanezumab in participants who experience signs of suicidal ideation or behavior.

Families and caregivers of participants being treated with fremanezumab should be instructed to monitor participants for the emergence of unusual changes in behavior, as well as the emergence of suicidal ideation and behavior, and to report such symptoms immediately to the study investigator.

The C-SSRS will be used to assess the patient's suicidal ideation (severity and intensity) and behavior (Posner et al 2011). The C-SSRS Baseline/Screening version will be completed by the patient at visit 1, and will be completed by the patient at every subsequent visit thereafter, including unscheduled visits. Any positive findings on the C-SSRS Since Last Visit version will require evaluation by a physician or doctoral-level psychologist.

A positive finding will be defined as a score ≥4: current suicide ideation with some intent to act, but no specific plan. In the case of a positive finding, the investigator, based on his medical judgment, will determine if the patient should be seen by a mental health specialist and if the patient should continue participation in the study. If the patient scores a 5: current suicide ideation with specific plan and intent, then the patient should be discontinued from the study immediately and seen by a mental health specialist.

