- g Currently menstruating information (yes, no, or not applicable) will be collected prior to blood and urine collection for laboratory tests for all females.
- h Height will be measured only at the screening visit.
- i Electrocardiograms (12-lead) will be performed in triplicate with approximately 1 to 5 minutes between recordings before blood draws and administration of questionnaires.
- j Oxygen saturation and respiratory rate will be measured in cases of suspected anaphylaxis and severe hypersensitivity.
- k Serum β-HCG and urine pregnancy tests are required for women of childbearing potential only.
-  The FSH test is required for postmenopausal women only.
- m Patients will enter headache days of any severity (mild, moderate, or severe), their duration, and prescription medication use into the electronic diary application daily throughout the pretreatment period and double-blind treatment periods. Eligible patients will upload the application to their own device or use the provisioned device and will be trained in its use and compliance requirements on the day of screening (visit 1). Patients will be asked to return the provisioned electronic diary device on visit 5 and the electronic tablet on visit 8 to the investigational center.
- n Blood samples for pharmacokinetic analysis (4 mL) will be collected prior to dosing at visit 2 (baseline). At each visit thereafter, a single blood sample for pharmacokinetic analysis will be collected prior to dosing, where applicable.
- o Blood samples for serum ADA assessment (5 mL) will be collected prior to dosing at each applicable visit and will also be collected upon observation of any anaphylaxis or severe hypersensitivity reaction.
- p Blood for further biomarker analyses will be collected after blood collection for pharmacokinetic and immunogenicity analyses as follows: 6 mL for serum, 6 mL for plasma, and 6.5 mL for PAXgene® RNA.
- q Patients will first complete the PHQ-2. If the PHQ-2 is positive (ie, a score of ≥3), they will complete the PHQ-9.
- The C-SSRS Baseline/Screening version will be completed at visit 1, and the Since Last Visit version will be completed at all other subsequent visits, including unscheduled visits.

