The onset and end dates, duration (in case of adverse event duration of less than 24 hours), action taken regarding IMP, treatment administered, and outcome for each adverse event must be recorded both on the source documentation and the CRF.

The severity, seriousness, and relationship of each adverse event to the test IMP and study procedures, as judged by the investigator, must be recorded as described below.

Further details are given in the Safety Monitoring Plan.

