#### 7.1.5.1. Definition of a Serious Adverse Event

A serious adverse event is an adverse event occurring at any dose that results in any of the following outcomes or actions:

- results in death
- is life-threatening adverse event (ie, the patient was at risk of death at the time of the event); it does not refer to an event which hypothetically might have caused death if it were more severe

- requires inpatient hospitalization or prolongation of existing hospitalization, which
  means that hospital inpatient admission or prolongation of hospital stay were required
  for treatment of an adverse event, or that they occurred as a consequence of the event
  Hospitalizations scheduled before the patient signed the ICF will not be considered
  serious adverse events, unless there was worsening of the preexisting condition
  during the patient's participation in this study.
- results in persistent or significant disability/incapacity (refers to a substantial disruption of one's ability to conduct normal life functions)
- is a congenital anomaly/birth defect
- an important medical event that may not result in death, be life-threatening, or require hospitalization but may jeopardize the patient and may require medical intervention to prevent one of the outcomes listed in this definition

Examples of such events are intensive treatment in an emergency room or at home for allergic bronchospasm, blood dyscrasias or convulsions that do not result in hospitalization, or the development of drug dependency or drug abuse. Note: Any suspected transmission of an infectious agent via a medicinal product is considered an important medical event.

All occurrences of possible drug-induced liver injury that meet Hy's law criteria, defined as all of the below, must be reported by the investigator to the sponsor as a serious adverse event:

- alanine aminotransferase (ALT) or aspartate aminotransferase (AST) increase of >3× the upper limit of normal (ULN)
- total bilirubin increase of >2× ULN
- absence of initial findings of cholestasis (ie, no substantial increase of alkaline phosphatase)
- no other explanation for the observed abnormalities

An adverse event that does not meet any of the criteria for seriousness listed above will be regarded as a nonserious adverse event.

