## 7.1.5.3. Reporting a Serious Adverse Event

## 7.1.5.3.1. Investigator Responsibility

To satisfy regulatory requirements, all serious adverse events that occur during the study, regardless of judged relationship to administration of the test IMP, must be reported to the sponsor by the investigator. The event must be reported within 24 hours of when the investigator learns about it. Completing the serious adverse event form and reporting the event must not be delayed, even if not all the information is available. The investigator does not need to actively monitor patients for adverse events once this study has ended.

Serious adverse events occurring to a patient after the last administration of IMP of that patient has ended but before the final study visit (visit 8) should be reported to the sponsor if the investigator becomes aware of them.

The serious adverse event form should be sent to the local safety officer (LSO) or designee (a contract research organization [CRO] in a country without a sponsor LSO) (contact information is in the Clinical Study Personnel Contact Information section); the LSO will forward the report to the sponsor's GPSP.

The following information should be provided to record the event accurately and completely:

- study number
- investigator and investigational center identification number
- patient number
- onset date and detailed description of adverse event
- investigator's assessment of the relationship of the adverse event to the test IMP (no reasonable possibility, reasonable possibility)

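### Protocol 7.12 defines a positive C-SSRS finding by ideation score alone, so on-treatment suicidal behavior with ideation below 4 does not trigger the required evaluation; the gap is small and cheap to close

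*Protocol*

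**What the plan says.** Protocol 7.12 gives the instrument a double purpose: "The C-SSRS will be used to assess the patient's suicidal ideation (severity and intensity) and behavior". It attaches a mandatory step to a positive result: "Any positive findings on the C-SSRS Since Last Visit version will require evaluation by a physician or doctoral-level psychologist". It then defines positive: "A positive finding will be defined as a score ≥4: current suicide ideation with some intent to act, but no specific plan". After a positive finding the investigator decides whether the patient should see a mental health specialist and whether to continue in the study. A score of 5, again described as ideation, requires immediate discontinuation, and withdrawal criterion 8 in Protocol 4.3 repeats that score.

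The same section also carries general wording that does cover behavior: patients are to be watched closely, families are to report changes, and "Consideration should be given to discontinuing fremanezumab in participants who experience signs of suicidal ideation or behavior".

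On timing, the C-SSRS footnote to Table 1 says that "the Since Last Visit version will be completed at all other subsequent visits, including unscheduled visits".

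SAP 8.6 repeats the evaluation requirement. It then describes patients with positive findings as those having either suicidal ideation or suicidal behavior, with no score threshold, in a sentence that sets up a data listing. SAP Section 17 records no changes from the protocol.

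**The concern.** The section says that the C-SSRS measures two things but builds its trigger from one. A patient who reports an aborted attempt or preparatory act since the last visit, and whose ideation is rated below 4, falls outside the definition. For that patient the mandatory evaluation and the explicit decision on referral and continuation do not follow from the C-SSRS answer.

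This is a patient-protection rule, so the stake is clinical. The protocol treats behavior as important elsewhere: exclusion r bars anyone with a lifetime history of it. The C-SSRS is also the only suicidality instrument scheduled between visits 3 and 7, because the PHQ-2/PHQ-9 is given only at visits 1 and 8, and the study has no Data Monitoring Committee.

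**Working it through.** No arithmetic applies. The check is to run each possible Since Last Visit result through the rules as written, and then to see what else in the protocol would act on it.

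**1. Which visits are in play.** The Since Last Visit version is used from visit 2 onward. At visit 2 it is completed before dosing, together with a review of eligibility (Appendix H), so behavior reported then already meets exclusion r. The rule therefore matters for visits 3 to 8.

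**2. The rule applied literally.**

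| Report at visits 3 to 8 | Positive under 7.12? | Evaluation required? | C-SSRS-based consequence |
|---|---|---|---|
| Ideation score 5 | Yes | Yes | Discontinue (7.12; 4.3 item 8) |
| Ideation score 4 | Yes | Yes | Investigator decides on referral and continuation |
| Ideation below 4, no behavior | No | No | None beyond the general wording |
| Ideation below 4, behavior reported | No | No | None beyond the general wording |

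The last row is the gap. The table assumes that the score in 7.12 is the ideation level, as its descriptions of 4 and 5 indicate. The instrument and its scoring are not in the documents.

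**3. Whether other text fills the last row.**
- *Other protocol definitions.* None adds behavior to a positive finding. Section 3.4 sends the reader to Appendix I for discontinuation criteria after positive C-SSRS findings, but Appendix I covers only liver tests.
- *SAP 8.6.* It includes behavior, but it tells the analyst what to list. It gives sites no instruction.
- *Adverse event rules.* Section 7.1.2 requires every adverse event to be recorded whatever its severity, and followed until it settles or care is handed over. It adds: "The severity, seriousness, and relationship of each adverse event to the test IMP and study procedures, as judged by the investigator, must be recorded". The seriousness criteria in 7.1.5.1 include "an important medical event that may not result in death, be life-threatening, or require hospitalization but may jeopardize the patient". For a serious event, 7.1.5.3.1 says "The event must be reported within 24 hours of when the investigator learns about it", and the investigator and sponsor both evaluate the report.
- *Withdrawal.* Protocol 4.3 item 7 allows withdrawal for an adverse event or other medical condition on the investigator's judgment. Section 3.4 lets the investigator or sponsor withdraw a patient for any reason.

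**4. What remains.** Behavior recorded as an adverse event, serious or not, receives clinical follow-up. What is missing is the evaluation that follows automatically from the C-SSRS answer, and the continuation decision attached to it. In the last row both depend on how the site handles the report.

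**The case against.** The strongest reply is that little is lost in practice. Suicidal behavior would ordinarily be recorded as an adverse event, and failure to record it would usually be a site error, not a fault in the plan. Even non-serious events are followed. Section 7.12 already calls for close observation and for discontinuation to be considered on signs of behavior, at any score. At a score of 4 the required step is evaluation by much the same clinicians, followed by the investigator's own judgment. The Safety Monitoring Plan cited in 7.1.2, which is not among the documents, may also cover behavior, as may any alert built into the electronic instrument named in the SAP.

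Most of this stands, and it limits the point to a small one. It does not remove it. Considering discontinuation is about stopping drug and does not require an evaluation, and classifying an aborted attempt or preparatory act is a judgment. The written rule still omits half of what the instrument is said to assess.

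A reader might infer that a patient reporting behavior would get no clinical attention. The adverse event and withdrawal provisions contradict that. A reader might also infer that the SAP's statement that it prevails over the protocol settles the matter. The SAP governs analysis and reporting and does not direct site action.

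**Conclusion.** The point holds as a low-severity wording gap: suicidal behavior reported at visits 3 to 8 with ideation below 4 does not, on the literal text, trigger the 7.12 evaluation or the explicit continuation decision. The number of patients affected cannot be derived from the documents. It is likely very few or none, since exclusion r removes patients with a known history. Counting scheduled questionnaires would not measure it, because such a count says nothing about how many patients report behavior.

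No efficacy or inferential result changes, and the SAP listing loses no data because its wording is already the broader one. A reader might take the point as a challenge to the cut-off of 4. It is not one: that threshold for ideation can be a deliberate choice, and nothing in the documents shows it to be wrong.

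The conclusion assumes that the unavailable Safety Monitoring Plan and electronic instrument do not already give sites a behavior trigger. If they do, citing them in 7.12 would be enough.

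**What to change.** In Protocol 7.12, define a positive finding as an ideation score of 4 or more, or any suicidal behavior reported on the Since Last Visit version. The existing evaluation and the investigator's decision on referral and continuation then apply to both. Keep the ideation cut-off.

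In Section 3.4, point to 4.3 and 7.12 for the C-SSRS criteria, not to Appendix I.

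In SAP 8.6, keep the broad listing. A flag for patients who are positive under 7.12 is optional.

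The change is one clause, but Appendix B means that it would normally need a written amendment with IRB approval, since a safety trigger is more than logistics or administration. It may bring a few extra evaluations by clinicians the protocol already designates. The benefit within this trial may be limited: recruitment stopped at 87 patients, and the study was planned to finish in Q2 2020.
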